## Reporting in eCRF

The date and time of last dose for IMP will be recorded in the eCRF. The primary reason for permanent discontinuation of IMP must be recorded in the medical records and on the end-of-treatment form in the eCRF where the following options are available:

- Pregnancy.
- Adverse event (if adverse event, a specification must be provided).
- Lack of efficacy.
- Withdrawal by subject.
- Lost to follow-up.
- Other (if other, a specification should be provided).

In case the primary reason is adverse event, the AE in question will be linked to the permanent discontinuation of IMP. To support the statistical analysis, it will also be recorded if the permanent discontinuation of IMP was due to the COVID-19 pandemic.

### 10.2.2 Reasons for temporary discontinuation of IMP

IMP dosing may be temporarily suspended in the event of:

- COVID-19 related disruption.

A decision to discontinue IMP temporarily or to reinstitute IMP treatment must be discussed with sponsor's medical expert. However, the investigator may suspend trial treatment at any time, even without consultation with sponsor's medical expert if the urgency of the situation requires immediate action and if this is determined to be in the subject's best interest. In such cases, sponsor's medical expert should be informed as soon as possible.

## 10.3 Early termination assessments

### Permanent discontinuation of IMP

Subjects who permanently discontinue IMP for any reason will be asked to attend an early termination visit as soon as possible after last administration of IMP and return to the trial site for additional visits as indicated below. See the schedule of trial procedures (Section 4) for data to be collected at these visits. Subjects who discontinue IMP but remain in the trial will continue completing the eDiary until the safety follow-up visit (Visit 16). The investigator will review any AEs which will be followed up according to Section 13.7, if the subject agrees.

Subjects who permanently discontinue IMP will be asked to attend:

THIS DOCUMENT CONTAINS CONFIDENTIAL INFORMATION AND MUST NOT BE COPIED OR MADE AVAILABLE TO ANY THIRD PARTY WITHOUT THE PRIOR WRITTEN CONSENT OF THE LEO PHARMA GROUP

- An early termination visit as soon as possible after last dose of IMP.
- The primary endpoint visit (16 weeks after randomisation).
- A safety follow-up visit (16 weeks after last administration of IMP).

Details on data to be recorded in the eCRF for subjects who permanently discontinue IMP can be found in Section 11.7.

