d) An end-of-trial form must be completed in the eCRF for all randomised subjects. See Section 11.7 for further details.

e) Subjects who permanently discontinue IMP prior to Week 16 and subjects who withdraw from the trial will be asked to come to an early termination visit and will be followed up as described in Section 10.3. As an early termination visit will only be performed in case of subjects permanently discontinuing the IMP, the visit has been marked with an (X).

THIS DOCUMENT CONTAINS CONFIDENTIAL INFORMATION AND MUST NOT BE COPIED OR MADE AVAILABLE TO ANY THIRD PARTY WITHOUT THE PRIOR WRITTEN CONSENT OF THE LEO PHARMA GROUP

- f) Unscheduled visit(s) between planned visits may be added to the subject's visit schedule if judged necessary by the investigator, e.g., due to an AE, a significant change in disease state, or difficulty complying with the clinical trial protocol requirements. At an unscheduled visit, the investigator should at least collect AEs data. Other assessments/procedures to be conducted at an unscheduled visit will be at the discretion of the investigator. As unscheduled visits will only be performed if judged necessary by the investigator, the visits have been marked with an (X).
- g) If the date of a trial visit does not conform to the clinical trial protocol, subsequent visits should be planned to maintain the visit schedule relative to randomisation/baseline.
- h) The informed consent form must be signed prior to performing any protocol-related procedures, including but not limited to screening evaluations and washout of disallowed medications.
- i) At screening, the demographic data listed in Section 11.2.1 will be recorded. At baseline, only age will be recorded.
- j) In case medical history is incomplete at the screening visit, missing data will be retrieved at Week 0 (baseline).
- k) *Mycobacterium tuberculosis* IFN- $\gamma$  release assay (or a PPD test if it is a requirement from the local health authorities).
- l) For women of childbearing potential (as defined in inclusion criterion no. 10 and 11, Section 8.2).
- m) In addition to the Q2W dosing schedule, both treatment groups will receive an additional dose of LEO 138559 450 mg or placebo at Week 1.
- n) All subjects must use an emollient twice daily (or more frequently, if needed) for at least 7 days before Day 1 (baseline) and throughout the treatment period (until Week 16).

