## Safety follow-up period (Week 16 to Week 32)

In the safety follow-up period, the subject will stop treatment with LEO 138559 or placebo injections and the safety of the subject will further be assessed at 3 safety follow-up phone calls (Weeks 20, 24, and 28) and at a final safety follow-up visit at Week 32. Topical treatment for AD will be permissible during the safety follow-up period.

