#### Laboratory tests performed at the trial site

Urine samples will be tested at the trial site with a dipstick according to the schedule of trial procedures (Section [4](#)). At an unscheduled visit, it will be at the discretion of the investigator if urine samples should be collected.

If a dipstick shows any abnormal reading, a urine sample must always be collected and sent to the central laboratory for further analysis, regardless of causality or investigator's assessment of significance.

THIS DOCUMENT CONTAINS CONFIDENTIAL INFORMATION AND MUST NOT BE COPIED OR MADE AVAILABLE TO ANY THIRD PARTY WITHOUT THE PRIOR WRITTEN CONSENT OF THE LEO PHARMA GROUP

Urine pregnancy tests for women of childbearing potential will be conducted at the trial sites. A woman with a positive urine pregnancy test at Week 0 (baseline) must not be randomised in the trial (inclusion criterion no. 10 and exclusion criterion no. 23). The test will be repeated every 4 weeks until Week 16 and at Week 32 as shown in the schedule of trial procedures in Section 4. A woman with a positive urine pregnancy test during the trial must immediately and permanently discontinue IMP and be withdrawn from the trial. A positive urine pregnancy test must be verified with a serum pregnancy test.

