### 13.2 Collection of adverse event reports

AE data must be collected from time of first trial-related activity after the subject has signed the ICF until completion of the clinical trial (all trial periods including safety follow-up visit at Week 32, see Section [7.3](#)).

AEs must be assessed by a physician. In the US only, certain AE assessments can be delegated to investigators with other qualifications. However, the diagnosis, seriousness, and causality of the AEs must be assessed by a physician.

At all visits, the subject will be asked a non-leading question by the investigator about AEs, for example: "How have you felt since I saw you last?" No specific symptoms should be asked for. It is important that the investigator also observes the subject for any changes not reported by the subject and records these changes.

Principles for data entry in the eCRF are described in Sections [11.4.1](#) to [11.4.5](#).

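### Subjects who stop IMP early but stay in the trial have three listed contacts, leaving 8 to 14 weeks with no scheduled AE enquiry against at most 4 weeks for subjects on schedule

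*Combined protocol and SAP*

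**What the plan says.** Section 10.3 separates subjects who stop IMP but agree to follow-up from those who withdraw altogether. For the first group it says "Subjects who permanently discontinue IMP will be asked to attend" three visits:

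- "An early termination visit as soon as possible after last dose of IMP";
- a return to the site at Week 16, counted from randomisation, for the primary endpoint;
- a final safety visit, timed at 16 weeks from the last dose.

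Panel 2 footnote e says that early stoppers "will be asked to come to an early termination visit and will be followed up as described in Section 10.3", so it adds nothing to that list. Footnote c adds only the Week 16 visit, which is already on it.

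For the follow-up period in general, Section 7.1 provides "3 safety follow-up phone calls (Weeks 20, 24, and 28) and at a final safety follow-up visit at Week 32". It speaks of the subject without qualification and does not mention early stoppers.

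Under Section 13.2, AEs are elicited at visits by a non-leading question: "No specific symptoms should be asked for". The investigator must also watch for changes that the subject does not report. Section 10.3 sends AEs in early stoppers to Section 13.7, which requires follow-up to outcome but sets no contact interval. For urine pregnancy tests, Section 11.4.5.2 says: "The test will be repeated every 4 weeks until Week 16 and at Week 32".

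**The concern.** AE counts compare fairly only if subjects are asked about AEs with similar regularity. Those who stay on schedule have a contact every 1 to 2 weeks to Week 16 and every 4 weeks afterwards. Those who stop IMP appear to drop to three contacts, however early they stop.

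Three things are at stake:

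- **Secondary endpoint.** It is the number of treatment-emergent AEs per subject from baseline to Week 16. For subjects who stop early, most of that window could pass without a scheduled enquiry.
- **AE rates.** Section 14.3.14.1 reports rates per 100 patient-years of observation. Time that is rarely enquired about counts fully in the denominator, so missed events lower the rate.
- **Event of special interest.** Lower respiratory tract infection needs its infectious cause and COVID-19 testing recorded (Panel 11). Those details are harder to recover months later.

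The three listed visits also cannot deliver the 4-weekly pregnancy testing in Section 11.4.5.2.

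**Working it through.** The plan gives no figure for the interval between AE contacts, so there is none to reproduce. Its only related figure is the attrition allowance in Section 14.1: 18 / (1 − 0.30) = 25.7, rounded up to 26 per arm. That reproduces.

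**Inputs**

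- Doses are given at Weeks 0, 1 and 2, then every 2 weeks to a final dose at Week 14 (Panel 2, Section 9.2). An early stopper's last dose L is therefore at Week 0, 1, 2, 4, 6, 8, 10 or 12.
- Contacts after stopping are early termination (ET), Week 16 and Week L + 16 (Section 10.3).
- Section 10.3 sets no limit on ET beyond as soon as possible. Assumption: it is varied from the day of last dose (ET = L) to 2 weeks later (ET = L + 2).
- Visit windows are ignored for both groups.

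**On schedule.** Contacts at Weeks 0, 1, 2, 4, 6, 8, 10, 12, 14, 16, 20, 24, 28 and 32 give gaps of 1 or 2 weeks to Week 16 and 4 weeks afterwards.

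**Early stoppers.** Gap A, before Week 16, is 16 − ET. Gap B, after Week 16, is (L + 16) − 16 = L. The longest gap is max(A, B). The last column adds the calls at Weeks 20, 24 and 28, up to the subject's own final visit.

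| L | A (ET = L + 2) | B | Longest, ET = L + 2 | Longest, ET = L | Longest with calls (ET = L + 2 / ET = L) |
|---|---|---|---|---|---|
| 0 | 14 | 0 | 14 | 16 | 14 / 16 |
| 1 | 13 | 1 | 13 | 15 | 13 / 15 |
| 2 | 12 | 2 | 12 | 14 | 12 / 14 |
| 4 | 10 | 4 | 10 | 12 | 10 / 12 |
| 6 | 8 | 6 | 8 | 10 | 8 / 10 |
| 8 | 6 | 8 | 8 | 8 | 6 / 8 |
| 10 | 4 | 10 | 10 | 10 | 4 / 6 |
| 12 | 2 | 12 | 12 | 12 | 4 / 4 |

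**Reading the table**

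- The longest gap is never below 8 weeks.
- For L = 0 to 6 it lies before Week 16, and the calls leave it unchanged.
- For L = 8 to 12 it lies after Week 16 (at L = 8 with immediate ET, both gaps are 8). The calls would cut it to 4 to 6 weeks for L = 10 and to 4 for L = 12. For L = 8 they help only if ET comes after the day of last dose.

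**If the final visit is at Week 32.** Section 10.3 also calls the final visit Visit 16, which Panel 2 places at Week 32. On that reading, gap B is 32 − 16 = 16 weeks for every early stopper without calls, and 4 weeks with them.

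**Subjects affected.** 0.30 × 26 = 7.8, about 8 per arm, if all attrition were IMP discontinuation with continued follow-up.

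**The case against.** A reader might infer four stronger claims. The documents do not support them.

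- **That early stoppers get no follow-up calls.** This rests on silence. The Section 10.3 list concerns visits to attend at the site, Section 7.1 excludes nobody from the calls, and the Visit 16 wording in Section 10.3 suggests the ordinary follow-up schedule. Whether the calls apply is unresolved.
- **That AEs in this group go unasked or rest on recall alone.** Known AEs are followed to outcome under Section 13.7, so an AE that caused stopping is not lost. Unscheduled visits must collect AEs. Section 13.2 requires observation as well as the question, and clinically significant examination, ECG and laboratory findings are reported as AEs. None of this sets a contact interval for new events, however, and the continuing eDiary records only itch.
- **That these subjects mostly stopped for safety.** Section 10.2.1 also lists lack of efficacy, withdrawal by the subject, loss to follow-up and other reasons, and no split is given.
- **That detection differs by arm.** Section 14.1 assumes 30% attrition in both arms. A difference is possible but not shown.

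Two limits on size also stand. For last doses at Weeks 8 to 12, the gap before Week 16 is only 6, 4 and 2 weeks with ET at 2 weeks, so the secondary endpoint is less exposed there. That endpoint is also only reported descriptively. None of this removes the gap before Week 16 for last doses at Weeks 0 to 6.

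**Conclusion.** The point holds as a matter of contact spacing. For any last dose from Week 0 to Week 12, the three listed visits leave a longest scheduled gap of 8 to 14 weeks with early termination 2 weeks after last dose, and up to 16 weeks if it is immediate. On schedule the maximum is 4 weeks. For last doses at Weeks 0 to 6 this does not depend on whether the Week 20, 24 and 28 calls apply; for Weeks 10 and 12 it does.

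The consequence is late or incomplete capture of new AEs in subjects who have been exposed to IMP. It is not loss of AEs already known.

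About 8 of 26 per arm is an upper bound, because attrition includes full withdrawal. Some stoppers are withdrawn outright, for example for pregnancy or a confirmed clinically significant ECG change (Sections 11.4.4 and 13.5.1).

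The result rests on the assumed timing of the early termination visit and on reading the Section 10.3 list as complete before Week 16. It is a cheap improvement worth making.

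**What to change.** In Section 10.3 and Panel 2 footnote e, add safety phone contacts for subjects who stop IMP but remain in the trial. Use the AE and concomitant-medication script of Visits 13 to 15. Place the calls so that no interval between scheduled contacts exceeds 4 weeks from the early termination visit to the final safety follow-up visit.

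The calls needed in a gap of g weeks are ceil(g/4) − 1, or none if g = 0. With early termination 2 weeks after last dose:

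- L = 0 or 1: gaps of 14 or 13 weeks need 3 calls, and the later gap needs none.
- L = 2 or 4: gaps of 12 or 10 need 2, and the later gap needs none.
- L = 6 or 8: gaps of 8 and 6 (in either order) need 1 each, so 2.
- L = 10 or 12: the earlier gap needs none, and gaps of 10 or 12 need 2.

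So each early stopper needs 2 or 3 calls.

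Do not waive calls that fall close to a site visit. For a last dose at Week 8, 4-weekly calls from early termination at Week 10 fall at Weeks 14, 18 and 22. Each is within 2 weeks of the visits at Weeks 16 and 24, so such a waiver would remove all three and leave the 8-week gap.

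State whether Visits 13 to 15 apply to these subjects. Reconcile Section 10.3 (Visit 16 against "A safety follow-up visit (16 weeks after last administration of IMP"), Panel 2, Section 7.1 and the pregnancy-test schedule in Section 11.4.5.2. How pregnancy testing is then arranged is for the sponsor to decide.

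The cost is a sentence, a footnote and a few short calls on the existing form: minor site time, with no new procedure.

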- o) Relevant concomitant medications/ concurrent procedures should be included from 3 months prior to screening until end of trial (Week 32).
- p) At Week 32, subjects will be asked to bring the eDiary back to the clinic.
- q) Completion of the eDiary for Worst Daily Pruritus NRS will be initiated at least 1 week prior to baseline (Day 1). Compliance with the eDiary completion will be reviewed by the trial site staff throughout the trial. Subjects who discontinue IMP but remain in the trial will continue completing the eDiary until the safety follow-up visit (Visit 16).
- r) At the screening visit (at the earliest Week -4), the subject's eligibility to participate in the trial must be confirmed before any PROs are completed. PROs will be collected in the electronic device at the trial site and should be completed before the investigator's assessment of efficacy.
- s) For the first 3 IMP treatment visits (i.e., Visits 3, 4, and 5) subjects will be monitored after IMP administration for immediate drug reactions for a minimum of 1 hour with vital signs taken immediately after IMP administration as well as after 30 minutes ( $\pm$  5 minutes) and after 1 hour ( $\pm$  5 minutes), or until stable, whichever is later.

THIS DOCUMENT CONTAINS CONFIDENTIAL INFORMATION AND MUST NOT BE COPIED OR MADE AVAILABLE TO ANY THIRD PARTY WITHOUT THE PRIOR WRITTEN CONSENT OF THE LEO PHARMA GROUP

- t) ECG should be recorded in triplicate for each time point and will be centrally evaluated.
- u) Urinalysis is performed by a urine dipstick. The analytes listed in Section 11.4.5 will only be measured if the urine dipstick is abnormal.

**Abbreviations:** ADA = anti-drug antibodies; AE = adverse event; BSA = body surface area; DLQI = Dermatology Life Quality Index; EASI = Eczema Area and Severity Index; ECG = electrocardiogram; eCRF = electronic case report form; HIV = human immunodeficiency virus; HRQoL = health related quality of life; IFN- $\gamma$  = interferon gamma; IgE = immunoglobulin E; IMP = investigational medicinal product; NRS = Numeric Rating Scale; PCR = polymerase chain reaction; PD = pharmacodynamics; PK = pharmacokinetics; POEM = Patient-Oriented Eczema Measure; PPD = purified protein derivative; PRO = patient-reported outcome; Q2W = every second week; SARS-CoV-2 = severe acute respiratory syndrome coronavirus 2; SFU = safety follow-up; vIGA-AD = validated Investigator Global Assessment Scale for Atopic Dermatitis.

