To compare the safety of LEO 138559 with placebo in subjects with moderate to severe AD.	
Secondary endpoint
 
 
• Number of treatment-emergent adverse events from baseline to Week 16 per subject.
 
 
Exploratory endpoint (ADA)
 
 
• Having a positive ADA response at Weeks 0, 4, 8, 12, 16, 32, assessed separately.
 

Exploratory objectives	
To evaluate the pharmacokinetics of LEO 138559 for 16 weeks in subjects with moderate to severe AD	
Exploratory endpoint (pharmacokinetics)
 
 
• Serum concentration of LEO 138559 at Weeks 0, 1, 2, 4, 6, 8, 10, 12, 14, 16, 32, assessed separately.
 

To evaluate the effect of treatment with LEO 138559 compared with placebo for 16 weeks on disease biomarkers in subjects with moderate to severe AD	
Exploratory endpoints (pharmacodynamics)
 
 
• Change in expression of AD disease biomarkers in serum from baseline to Week 16.
 
• Change in expression of AD disease biomarkers in skin from baseline to Week 16.
 

**Abbreviations:** AD = atopic dermatitis; ADA = anti-drug antibodies; DLQI = Dermatology Life Quality Index; EASI = Eczema Area and Severity Index; EASI 50 = at least 50% decrease in EASI score; EASI 75 = at least 75% decrease in EASI score; EASI 90 = at least 90% decrease in EASI score; NRS = numeric rating scale; POEM = Patient-Oriented Eczema

Measure; TCI = topical calcineurin inhibitor(s); TCS = topical corticosteroid(s); vIGA-AD = Validated Investigator Global Assessment Scale for Atopic Dermatitis.

THIS DOCUMENT CONTAINS CONFIDENTIAL INFORMATION AND MUST NOT BE COPIED OR MADE AVAILABLE TO ANY THIRD PARTY WITHOUT THE PRIOR WRITTEN CONSENT OF THE LEO PHARMA GROUP

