### 7.3 End-of-trial definition

A subject is considered to have completed the trial if they have completed all periods of the trial including the safety follow-up visit at Week 32 (see Section [11.7](#) for data to be recorded on the end-of-trial form).

The end of the trial is defined as the date of the last safety follow-up visit (Week 32) for the last subject in the trial globally.

Final data collection for evaluation of the primary endpoint will occur at Week 16. Therefore, the primary completion date is defined as the date of last Week 16 visit for the last subject in the trial globally.

THIS DOCUMENT CONTAINS CONFIDENTIAL INFORMATION AND MUST NOT BE COPIED OR MADE AVAILABLE TO ANY THIRD PARTY WITHOUT THE PRIOR WRITTEN CONSENT OF THE LEO PHARMA GROUP

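### Section 10.3 dates the safety follow-up visit of subjects who stop IMP early at 16 weeks after last dose, which conflicts with Visit 16 (Week 32) elsewhere and ends 14 days before the 18-week safety windows

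*Combined protocol and SAP*

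**What the plan says.** Section 10.3 says that subjects who permanently discontinue IMP will attend an early termination visit and "return to the trial site for additional visits as indicated below". The list that follows contains the early termination visit, the primary endpoint visit 16 weeks after randomisation, and "A safety follow-up visit (16 weeks after last administration of IMP"). It does not mention the phone calls.

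The same section says that subjects who stop IMP but stay in the trial "will continue completing the eDiary until the safety follow-up visit (Visit 16"), and Panel 2 footnote q repeats this: "Subjects who discontinue IMP but remain in the trial will continue completing the eDiary until the safety follow-up visit (Visit 16"). Panels 1 and 2 define Visit 16 as Week 32 (Day 225).

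Other sections give Week 32 only:
- Section 7.1 describes the follow-up period as "3 safety follow-up phone calls (Weeks 20, 24, and 28) and at a final safety follow-up visit at Week 32".
- Section 7.3 counts subjects as completers if "they have completed all periods of the trial including the safety follow-up visit at Week 32".
- Section 11.7 records attendance at the safety follow-up visit against Week 32 for all randomised subjects. The possible last visits it names are Week 32, early termination and primary endpoint.
- Section 13.2 requires AE collection up to and including the Week 32 visit.
- For urine pregnancy tests, Section 11.4.5.2 says "The test will be repeated every 4 weeks until Week 16 and at Week 32".
- The ADA endpoint in Panel 3 is "Having a positive ADA response at Weeks 0, 4, 8, 12, 16, 32, assessed separately".

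Two windows run for 18 weeks after last dose: the limit for calling an AE treatment-emergent (Section 14.3.14.1) and the minimum contraception period (inclusion criterion 11).

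Two places lean towards the bullet. Panel 2 footnote e refers early stoppers to Section 10.3 for their follow-up, and Section 12.1 calls a 16-week follow-up after last dose appropriate.

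**The concern.** One visit has two dates. A site that follows the bullet sees the subject for the last time between Week 16 and Week 28; a site that follows the Visit 16 label sees the subject at Week 32. Different sites can reasonably do different things. Observation time in the Week 0 to 32 and Week 17 to 32 AE tables would then vary for a reason unrelated to treatment.

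The earlier date also ends on-site follow-up before the protocol's own 18-week windows close. Some of these subjects will have stopped because of an AE, so they are a group in whom complete safety follow-up matters. ADA samples and site pregnancy tests are tied to site visits and cannot be replaced by a phone call.

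**Working it through.** **Inputs.** Last planned dose Week 14 = Day 99, and Visit 16 = Week 32 = Day 225 (Panel 2). Dosing weeks before Week 14: 0, 1, 2, 4, 6, 8, 10, 12. Calls at Weeks 20, 24, 28. Visit window ±3 days. Bullet interval 16 weeks (Section 10.3). Safety windows 18 weeks (Section 14.3.14.1 and inclusion criterion 11).

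**Reproducing the schedule.** With Day = 7 × Week + 1, Week 14 is Day 99 and Week 32 is Day 225. Subjects who finish dosing are followed for 225 − 99 = 126 days = 18 weeks after last dose, which equals both windows.

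**Shortfall under the bullet.** 16 × 7 = 112 days; 126 − 112 = 14 days. With the visit window, the range is 126 − 115 = 11 days to 126 − 109 = 17 days.

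**By week of last dose (L).** Bullet visit = L + 16; window closes = L + 18; gap between the two dates = 32 − (L + 16) = 16 − L weeks; Week 32 falls 32 − L weeks after last dose.

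| L | Bullet visit (week) | 18-week window closes (week) | Bullet to Week 32 (weeks) | First call at or after closing (week) | Week 32, in weeks after last dose |
|---|---|---|---|---|---|
| 0 | 16 | 18 | 16 | 20 | 32 |
| 1 | 17 | 19 | 15 | 20 | 31 |
| 2 | 18 | 20 | 14 | 20 | 30 |
| 4 | 20 | 22 | 12 | 24 | 28 |
| 6 | 22 | 24 | 10 | 24 | 26 |
| 8 | 24 | 26 | 8 | 28 | 24 |
| 10 | 26 | 28 | 6 | 28 | 22 |
| 12 | 28 | 30 | 4 | none | 20 |

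The bullet never gives Week 32. For a last dose at Week 0 it coincides with the primary endpoint visit (Day 113), so no site visit follows Week 16. Keeping Visit 16 at Week 32 covers 18 weeks for everyone.

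**If the calls continue.** A call falls at or after the close of the window for every last dose from Week 0 to Week 10. For Weeks 2, 6 and 10 it falls on the closing date, so up to 3 days may be missed if it is made early in its window. For Week 12 the last call and the bullet visit are both at Week 28, leaving 14 days to Week 30.

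**Size in patient-years.** The number of early stoppers who stay in the trial is not given. As an illustration, the 30% planning attrition gives 2 × (26 − 18) = 16 subjects: 16 × 14 = 224 days = 0.61 patient-years. With 8 subjects: 8 × 14 = 112 days = 0.31 patient-years. Planned observation with no dropout is 52 × 224 = 11,648 days = 31.9 patient-years, so these are 1.9% and 1.0%. Because the denominator ignores dropout, the percentages show order of magnitude only.

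**The case against.** The best defence is that Section 10.3 is the specific rule. Footnote e hands early stoppers to it, and Section 12.1 supports a 16-week interval after last dose. On that view, Visit 16 is just the name of the follow-up visit, held on whatever date 10.3 gives. Section 11.7 also foresees participation ending before Week 32. This softens the footnote q conflict but does not remove the problem: the 11.7 attendance item and 13.2 still give Week 32, and no last-visit option in 11.7 fits a visit 16 weeks after last dose. The 12.1 figure does not match the schedule either, which gives 18 weeks after the Week 14 dose. Sixteen weeks is right only when counted from Week 16.

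Other parts of the defence stand. The 18-week AE limit classifies events; nothing requires a visit on the day it closes. AEs are also reported as rates per 100 patient-years, which allows for shorter observation. Contraception is the subject's obligation and does not depend on a visit.

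Some stronger readings are tempting but not supported:
- *AEs late in the window are lost for all early stoppers.* Section 13.2 requires collection to Week 32, and the AE row of Panel 2 covers the phone visits with no exemption for subjects off IMP. A loss arises only where sites stop at the bullet date.
- *The bullet costs these subjects their completer status.* Section 7.3 requires all trial periods, treatment included, so an early stopper arguably fails it on either date.
- *Pregnancy reporting ends early.* Section 13.5.1 ties that duty to completing the trial; only the last scheduled test moves.
- *Sixteen subjects is an upper limit.* The 30% is a planning assumption, not a bound. It need not equal the number who stop IMP and remain, since those who withdraw are asked only for an early termination visit.

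**Conclusion.** The plan is inconsistent as written. Section 10.3 dates the visit 4 to 16 weeks before the Week 32 date used in Panels 1 and 2 and in Sections 11.7 and 13.2. On the 10.3 date, the final site visit, ADA sample and pregnancy test fall 14 days (11 to 17 with the visit window) before the 18-week windows close, and a subject seen only then has no Week 32 ADA sample.

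The AE consequence depends on conduct. If sites apply 13.2 and continue the calls, mainly a last dose at Week 12 is left short. If they stop at the bullet date, every early stopper is short by about two weeks. Even on the illustrative 16 subjects, this is about 0.61 patient-years.

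The effect is limited to the descriptive safety tables that run past Week 16 and to ADA and pregnancy follow-up of early stoppers. The primary endpoint and the secondary endpoint, both ending at Week 16, are unaffected. The point is minor in size but should be corrected, because it determines when subjects are seen and sampled.

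**What to change.** Preferred: in Section 10.3, replace the bullet with *A safety follow-up visit (Visit 16, Week 32).* and add *The safety follow-up phone calls (Visits 13 to 15, Weeks 20, 24 and 28) continue for subjects who remain in the trial.* This agrees with 7.3, 11.7, 13.2 and footnote q.

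Alternative: set the visit at 18 weeks after last dose and align 7.3, Panel 2 with footnote q, 11.7 and 13.2. The visit would then fall at Weeks 18 to 30, so the Week 32 ADA endpoint would need a rule for these subjects.

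Either way, correct the 16-week wording in Section 12.1.

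The cost is a few sentences in an amendment. The preferred fix adds no procedure, since the visit and the calls are already in Panel 2. The downside is a later final visit for subjects already off drug: 4 to 16 weeks later under Week 32, 2 weeks later under the 18-week option. Some may not return. Under Week 32 their last ADA sample and pregnancy test would come 20 to 32 weeks after last dose, against 18 for subjects who finish dosing.
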